8.2.4 ADVERSE EVENT REPORTING

Event Type	Report To DSMB	Reporting Timeframe
Adverse Event	Summary Report	Annually
Unanticipated Problem	IRB Unanticipated Problem Report	Report within 10 business days
	NIMH Unanticipated Problem Report	Report within 10 business days
IRB Determination is Serious or Continuing Noncompliance	NIMH Noncompliance Report	Report within 10 business days of IRB determination
IRB Determination is Study Suspension or Termination	NIMH Study Suspension Report	Report within 3 business days of IRB determination
Protocol Deviation	Summary Report	Annually

8.2.5 SERIOUS ADVERSE EVENT REPORTING

Event Type	Nature of Event	Study Related	Report To	Reporting Timeframe
Serious Adverse Event	Unexpected	The event is related	IRB Serious Adverse Event Report	Report within 10 business days

		(possibly, probably, definitely related) to the research	NIMH Serious Adverse Event Report	Report within 10 business days
Serious Adverse Event	Expected	Related or Unrelated	DSMB	Report 3 times a year
Serious Adverse Event	The Nature of Event is: “Suicide resulting in death” OR “Death (not suicide or unsure if suicide)”	The death is related (possibly, probably, or definitely related) to the research	NIMH Death Report	Report no later than within 5 business days
Serious Adverse Event	The Nature of Event is: “Suicide resulting in death” OR “Death (not suicide or unsure if suicide)”	The death is definitely not related to the research	DSMB	Report 3 times per year

8.2.6 REPORTING EVENTS TO PARTICIPANTS

If our Single IRB determines that an Adverse Event or Serious Adverse Event needs to be reported to an individual study participant, one of the multiple PIs will telephone that person and notify them of the event and explain the risk. If our Single IRB determines than an Adverse Event or Serious Adverse Event needs to be reported to all study participants, notifications will be emailed and mailed to study participants.

8.3 UNANTICIPATED PROBLEMS, PROTOCOL DEVIATIONS, AND NON-COMPLIANCE

8.3.1 DEFINITION OF UNANTICIPATED PROBLEMS

Definitions

1. Unanticipated Problems:

- a. Unexpected in terms of nature, severity, or frequency, given the research procedures that are described in the protocol-related documents, such as the IRB-approved

research protocol and informed consent document and (b) the characteristics of the subject population being studied

- b. Related or possibly related to a subject's participation in the research
- c. Suggests that the research places subjects or others at a greater risk of harm (including physical, psychological, economic, or social harm) related to the research than was previously known or recognized.

2. **Protocol Deviation:** An accidental or unintentional change to the IRB-approved protocol that may cause harm to subjects or others, indicates that the subjects or others are at an increased risk of harm, or has adversely impacted data integrity. *Protocol deviations will be reported to the Single IRB as either an unanticipated problem or noncompliance.*

3. **Noncompliance:** any action or activity associated with the conduct or oversight of research involving human subjects that fails to comply with applicable regulations, the IRB's *Handbook*, and/or the determinations and requirements of the IRB. Noncompliance may range from minor to serious; be unintentional or willful; and may occur once, sporadically, or continuously.

- a. **Serious Noncompliance:** any action or omission in the conduct or oversight of research involving human subjects that affects the rights and welfare of subjects, increases risk to subjects, or compromises the scientific integrity or validity of the research.
- b. **Continuing Noncompliance:** a pattern of repeatedly failing to comply with applicable regulations, the IRB's *Handbook*, and/or the determinations and requirements of the IRB that may affect subjects' rights and welfare, increase risk to subjects, or may compromise the scientific integrity or validity of the research. Continuing noncompliance also includes frequent instances of minor noncompliance or failure to respond to a request to resolve an episode of noncompliance.

8.3.2 PROBLEM REPORTING

Unanticipated problems, protocol deviations, or instances of non-compliance will be reported to our Single IRB within 10 business days, along with any corrective actions that have been or will be taken. Our Single IRB will determine whether an unanticipated problem, protocol deviation, or instance of non-compliance needs to be reported to an individual or to all study participants. All Unanticipated Problems, protocol deviations, or instances of non-compliance will be compiled and reported to the NIMH DSMB as per the adverse event reporting table above.

It will be the responsibility of the site investigator to use continuous vigilance to identify and report deviations to the Single IRB. As specified in **Section 8.3.5, Adverse Event Reporting**, the PIs will report protocol deviations to the Single IRB that are considered to be *unanticipated problems* or *noncompliance* within 10 business days. The PI will be responsible for knowing and adhering to any actions required by the Single IRB, including modifying the protocol and/or report to the NIMH and the NIMH DSMB, as noted in the event reporting table above.

8.3.3 REPORTING PROBLEMS TO PARTICIPANTS

If our Single IRB determines that an unanticipated problem, protocol deviation, or instance of non-compliance needs to be reported to an individual study participant, will telephone that person and notify them of the event and explain the risk. If our Single IRB determines than an unanticipated problem, protocol deviation, or instance of non-compliance needs to be reported to all study participants, notifications will be emailed and mailed to study participants.

9 STATISTICAL CONSIDERATIONS

9.1 STATISTICAL HYPOTHESES

Hypotheses for Primary Objective (Effectiveness Trial)

Hypothesis a: *Compared to patients with MHS and OUD at clinics randomized to the control, patients at clinics randomized to the intervention group (both Cohorts 1 and 2) will report better access to and engagement in OUD treatment, less opioid use (primary outcome), better mental health functioning (primary outcome), fewer disorder specific mental health symptoms, better quality of life, and fewer risk factors for premature mortality.*

Hypothesis b: *Engagement in MOUD will completely mediate any improvements in patient reported outcomes observed in intervention clinics compared to control clinics.*

Hypothesis for Secondary Objective (Pre-Post Trial)

Hypothesis: *The proportion of patients enrolled in the clinic with a MH diagnosis and a new OUD diagnosis documented in the electronic medical record will be higher in the post-period than the pre-period.*

Exploratory Hypothesis for Exploratory Objective (Pre-post evaluation)

[figure not shown]
Exploratory Hypothesis : *CHAMP intervention clinics receiving the high-intensity sustainability implementation strategy will maintain their implementation outcomes (adoption, reach, intervention fidelity and effectiveness) after the effectiveness trial has been completed (post) compared to during the effectiveness trial (pre).*

9.2 SAMPLE SIZE DETERMINATION

Power Analysis For Pre-Post Trial – Under the assumption of 24 clinics, at least 500 eligible MHS patients in each clinic in each six-month period, a rate of documented OUD of 1% pre-screening, a conservative estimate of 0 correlation between pre- and post-percentages, and an alpha significance level of 0.05, we will have 80% power to detect an increase from a pre-screening percentage of 1% to a post-period percentage of 1.7%.

Power Analysis For Effectiveness Trial - Assuming a coefficient of variation of 0.33 for the continuous outcome of days of illicit opioid use⁶⁷⁶ and SF12V MCS scores⁶⁶⁸⁷, a highly conservative intraclass correlation within clinics of 0.03, 12 clinics per group and 40 patients per clinic (n=960, accounting for NIH Behavioral and Social Intervention Clinical Trial Protocol Template v3.0 - 20180827

20% attrition), we will have 80% power to detect an effect size of 0.31. We chose to use a highly conservative intraclass correlation to ensure sufficient power for secondary outcomes and mediation analyses (Hypothesis 2b). Thus, conservatively we will have 80% power to detect a 10 % difference in number of days using illegal opioids in the past month (e.g., 15.00 days compared to 13.5 days) and 10% difference in MCS scores (e.g., 40 compared to 36) between CHAMP and CoCM for MHS only clinics. Because these are multiple primary outcomes (and not co-primary outcomes), this power analysis assumes a Bonferroni correction for the two multiple primary outcomes. Specifically, the intervention will be interpreted to have been successful if there is a significance group different between either primary outcome, not both primary outcomes. Because of recruitment challenges, power analyses are also now provided for the lower bounds of expected enrollment. The lower-bounds power analysis assumes that we will recruit 360 study participants instead of 1200. For this lower-bounds power analysis, we assume a more realistic intraclass correlation of 0.01 instead of 0.03. Collaborative care trials conducted by [name] (MPI) and [name] (NIMH collaborator) found intraclass correlation coefficients in the range of 0.008-0.001).^{30,66} Assuming a coefficient of variation of 0.33 for the continuous outcome of days of illicit opioid use⁶⁷ and SF12V MCS scores⁶⁸, an intraclass correlation within clinics of 0.01, 12 clinics per group, 15 patients enrolled per clinic (n=288 accounting for 20% attrition), we will have 80% power to detect an effect size of 0.41. The sample size of 360 does not represent a revised enrollment target, and we will continue to enroll as many study participants as possible (up to 1,200) using enhanced recruitment methods and by extending the recruitment period if possible.

9.3 POPULATIONS FOR ANALYSES

Intention-to-Treat

9.4 STATISTICAL ANALYSES

9.4.1 GENERAL APPROACH

Statistical Analysis Plan - There will be a formal Statistical Analysis Plan that will be completed prior to unblinding of the Effectiveness trial data. The statistical plan will be posted publicly or registered before the study begins.

Reporting of Descriptive Statistics – Categorical data collected at baseline will be presented as percentages. Continuous data will be presented as means with standard deviations.

Statistical Tests – An alpha level of 0.05 and two-tailed tests will be used to determine statistical significance.

Covariates – Covariates will be included if they are theoretically related to both the dependent variable and the probability of having missing data, and will be specified later in the SAP.

Test of Distributional Assumptions – We will examine residuals for normality. If residuals are not approximately normally distributed, we will use a sandwich estimator (e.g., robust maximum likelihood estimator) to correct standard errors. Note that the treatment effect is a binary indicator and consequently, the point estimate for treatment condition will be unbiased, conditional on other model effects being specified correctly. For continuous covariates, we will examine scatterplots and partial regression plots to ensure the linearity assumption is reasonable. If linearity appears to be meaningfully violated, we will transform either the predictor variables or the outcome, depending on the patterning of nonlinearity.

9.4.2 ANALYSIS OF THE PRIMARY ENDPOINT(S)

Primary Outcomes of Effectiveness Trial - The *multiple* primary outcomes evaluated will be patient-reported measures of illicit opioid use, and mental health functioning. *Opioid use* will be measured using item 7E from the Brief Addiction Monitor (BAM)⁶⁸: “*In the past 30 days, how many days did you use opiates such as Heroin, Morphine, Dilaudid, Demerol, Oxycontin, oxy, codeine (e.g., Tylenol 2,3,4), Percocet, Vicodin, Fentanyl, etc.? Do not count times you used buprenorphine, suboxone, or methadone as directed by a healthcare provider.*” Mental health functioning will be measured using the Mental Component Summary score of the SF-12.

Intent to Treat Analysis of Primary Outcomes of Effectiveness Trial – Given the cluster-randomization we will use appropriate mixed models (also known as multi-level models) to account for clinic effects that are shared by subjects from the same clinic. Measurement occasions (level 1) will be nested within individuals (level 2) which are then nested within clinics (level 3). All outcomes will be analyzed with a multilevel model accounting for clustering of observations (level 1) within patients (level 2) and clinics (level 3). The model will include a random intercept and random linear slope to account for person-level clustering and repeated measures on individual subjects over time that may be associated with variable time trends across participants. To allow for curvilinear change over time, time will be entered as a nominal variable by including dummy codes for the 3- and 6-month time points. The explanatory

variable of interest will be group randomization status (e.g., intervention versus control). Main effects and interaction terms with time-indicator variables capture the difference between intervention and control group at each wave. Covariates will be included if they are theoretically related to both the dependent variable and the probability of having missing data. An alpha level of 0.05 and two-tailed tests will be used to determine statistical significance. Results will be presented as adjusted differences between groups with confidence intervals. **Missing Data** - We will examine patterns of missing data to determine the degree to which the missing at random assumption (the degree to which missingness is related to variables included in the model) is plausible. With high missing rates, we may use missing data methods to account for missing not at random mechanisms. If warranted, multiple imputation or similar methods will be used to account for missing data on completed or partially completed baseline and follow-up surveys (e.g., skipped items).

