Integrated Treatment – The treatment of OUD will be integrated with the treatment of MHS, other substance use disorders (SUDs), and physical health disorders. **Team-Based:** The integrated care team will include a care manager, primary care providers and consulting psychiatrist. Consulting psychiatrists will have a buprenorphine waiver and be trained by MPI [name]. **Patient-Centered:** The care manager will educate, activate, promote self-management, assess treatment preferences, and engage in shared decision making. **Population-Based:** The care manager will enter patients in the CMTS registry and conduct outreach activities with those who miss appointments. **Measurement-Based:** OUD, other SUD, and MHS will be assessed over time and stored in CMTS. Care managers will use the PHQ-9 for depression, the GAD-7 for anxiety and the PCL-5 for posttraumatic stress disorder (PTSD). For patients not experiencing a 50% decrease in symptom severity, options for “treating to target” include: 1) increasing dose, 2) switching medications, 3) augmenting medications, and/or 4) intensifying psychosocial interventions. Treatment adherence and side effects will also be monitored and managed. Monitoring OUD symptoms and adherence is described below. **Evidence-based:** The primary care provider will prescribe FDA approved psychotropic medications for depression, anxiety and PTSD concurrently with pharmacologic treatment of OUD (as described below). Care managers will also be

trained to deliver Behavioral Activation (described below). For alcohol, the primary care provider will prescribe one of two FDA approved medications (disulfiram or acamprosate) that can be used with buprenorphine. The care manager will use the AUDIT-C⁵² for measurement based care. For benzodiazepines, the care manager will screen for anxiety and sleep disorders, and if present the consulting psychiatrist will recommend a trial of an SSRI or trazodone. For other SUDs, we will deliver Behavioral Activation and encourage abstinence. Primary care providers will offer appropriate management of physical health disorders common among patients with OUD and MHS such as chronic obstructive pulmonary disease, viral hepatitis, human immunodeficiency virus, and chronic pain.

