
			
7.Because we have determined that we may not be able to obtain data from the state Prescription Drug Monitoring Programs, we are now using chart review to identify prescriptions for opioids written in the primary care clinic.
 
8.We broke up the safety plan question into separate questions in an attempt to encourage survey respondents to agree to the best safety plan (the questions are now ordered by our ranking of safety).
 
9.The PDS-5 had inferior face-validity than the PCL-5
 
10.The 13 months from today was a typo. Also, we wanted to be able to collect pre-baseline opioid prescription information from the chart review and the Prescription Drug Monitoring Program.

4	3.17.21	
1. Clarifying the language for patient eligibility exclusion criteria to clarify that we will:
 
 a. allow patients receiving a current prescription if the prescriber is an addiction specialist and is a primary care provider in the clinic or health system). b. who are or have been enrolled in CoCM for co-occurring disorders for more than 14 days because their baseline survey responses will not be documented prior to receiving the intervention. 
2. Adding information to Virtual e-consenting process to clarify that the and the patient can receive the e-consent form via text and will receive an signed PDF of the e-consent form via email or text.
	
1. to clarify the exclusion criteria for the clinics and to make study criteria more inclusive.
 
2. Required by the IRB to clarify the e-consent process in the ICF and the protocol.

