Primary outcome. There are two primary outcomes (see Table 1). Opioid use is one of our primary outcomes and is measured using item 7E from the Brief Addiction Monitor-Revised (BAM-R) which was derived from the Addiction Severity Index35 by CESATE: “7. In the past 30 days, how many days did you use any of the following drugs: E. Opiates (e.g., Heroin, Morphine, Dilaudid, Demerol, Oxycontin, oxy, codeine (Tylenol 2,3,4), Percocet, Vicodin, fentanyl, etc.)?” Our other primary outcome is mental health related quality of life and is being measured using

the Veterans Short Form Health Survey 12 Mental Health Component Summary score (MCS). Both primary outcomes are assessed at the 6-month follow-up survey.

Secondary outcomes. This study includes 24 secondary outcomes, assessed at both the 3-month follow-up and the 6-month follow-up (Table 1). Secondary outcomes include the use of other drugs, depression, anxiety, PTSD, pain, physical health-related quality of life and perceived access to OUD care (see Table 1). Secondary outcomes also include opioid use and mental health related quality of life assessed at the 3-month follow-up survey. Exploratory outcomes are risk factors for premature mortality, including suicidal ideation, discontinuing MOUD, overdose, suicide attempts, emergency department admission, and hospitalization. Risk factors are collected via survey and adverse event reporting.

Construct/Instrument	Instrument(s)	Baseline	3-Month Follow-Up	6-Month Follow-Up
Multiple Primary Outcomes				
Opioid Use	BAM-R ^{1,2}	X	X	X
Mental health related quality of life (MCS)	Veterans Short Form-12 ³	X	X	X
Secondary Outcomes				
Pain	PEG ⁴	X	X	X
Alcohol Use	AUDIT-C ⁵	X	X	X
Cannabis Use	BAM-R ^{1,2}	X	X	X
Other Drug Use	BAM-R ^{1,2}	X	X	X
Depression	SCL-20 ⁶	X	X	X
Anxiety	PROMIS Measure - Anxiety, Short Form ^{7,8}	X	X	X
PTSD	PCL-5 ^{9,10}	X	X	X
Physical health related quality of life (PCS)	Veterans Short Form-12 ³	X	X	X
Access to Care	APAC ¹¹	X	X	X
Exploratory Outcomes				
Risk factors for mortality	WFS ¹ and Adverse Events	X	X	X
Mediator Variable				
MOUD Consistency	WFS ¹	X	X	X

APAC - Assessment of Perceived Access to Care

BAM-R - Brief Addiction Monitor-Revised

ICR - Individual Change Readiness

MOUD – Medications for Opioid Use Disorder

PCL-5 - PTSD Check List

PC-PTSD-5 – Primary Care PTSD Screen for DSM-5

PCS - Physical health related quality of life

PEG - Pain, Enjoyment of Life and General Activity

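### The opioid primary outcome is labelled illicit use, but its item also counts analgesics taken as prescribed, and Protocol and SAP differ on whether MOUD days are exempt

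*Protocol*

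**What the plan says.** Protocol 9.4.2 introduces the two primary outcomes as "patient-reported measures of illicit opioid use, and mental health functioning". Protocol 9.2 powers the trial for days of illicit use and states the target as a "10 % difference in number of days using illegal opioids in the past month".

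The item in 9.4.2 has a 30-day recall window and its question reads "how many days did you use opiates such as Heroin, Morphine, Dilaudid, Demerol, Oxycontin, oxy, codeine (e.g., Tylenol 2,3,4), Percocet, Vicodin, Fentanyl, etc". It has one exemption: "Do not count times you used buprenorphine, suboxone, or methadone as directed by a healthcare provider". SAP section 3 gives the drug list as "E. Opiates (e.g., Heroin, Morphine, Dilaudid, Demerol, Oxycontin, oxy, codeine (Tylenol 2,3,4), Percocet, Vicodin, fentanyl, etc" and quotes no exemption of any kind.

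Protocol 5.2 does not exclude patients who are prescribed opioid analgesics. Protocol 6.1.1 names, among physical disorders common in this population, "viral hepatitis, human immunodeficiency virus, and chronic pain". Under 6.1.1 intervention clinics add MOUD, mainly buprenorphine/naloxone. The control model refers OUD care to specialty settings, although control primary care providers may also prescribe MOUD.

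Prescribed-opioid status appears nowhere in the SAP: not among the section 4.1 covariates, not as a row in Table S1, and not in any analysis.

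**The concern.** The label and the instrument describe different constructs. The item records days of any listed opioid, with or without a prescription, apart from MOUD in the Protocol's wording. A reduction on this item cannot by itself be reported as a reduction in illicit use.

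The mismatch may also not be neutral between arms. Under the Protocol wording, prescribed analgesic days score as outcome days and prescribed MOUD days do not, and MOUD is what the intervention adds. Under the SAP wording, a respondent could count buprenorphine days as opiate days, which would hide real improvement where MOUD is used more. At stake are what the trial may claim from one of its two primary outcomes and, to an unknown degree, the size and direction of the estimate.

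**Working it through.** **1. How the two wordings score the same patient.** Days in the past 30, baseline to follow-up:

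| Patient | Protocol wording | SAP wording, if buprenorphine is counted |
|---|---|---|
| Daily analgesic as prescribed throughout | 30 to 30 | 30 to 30 |
| Daily prescribed analgesic, then daily buprenorphine as directed | 30 to 0 | 30 to 30 |
| Daily heroin, then daily buprenorphine as directed | 30 to 0 | 30 to 30 |

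Under the Protocol wording, rows 2 and 3 look alike although illicit use changes only in row 3. Under the SAP wording read this way, neither shows a change. If SAP-wording respondents leave buprenorphine out, the two columns agree.

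**2. The SAP's detectable difference.** Inputs from SAP sections 4.1 and 6: 254 patients, 28 clinics, opioid-use ICC 0.00, effect size 0.40, difference 2.65 days, two-sided alpha 0.025 per outcome.

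- Standardised SE = sqrt(4 × 1 / 254) = 0.1255, with a design effect of 1 because the ICC is 0.
- Noncentral t with 28 − 2 = 26 degrees of freedom: power at 0.40 is 78.5%, close to the stated 80%.
- Implied SD = 2.65 / 0.40 = 6.63 days.

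The 2.65-day figure is therefore a reasonable yardstick.

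**3. How much switching would equal 2.65 days with illicit use equal in both arms.** Shift in mean days = net between-arm excess of patients switched × counted days dropped per patient.

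- 30 days dropped: 2.65 / 30 = 8.8%
- 20 days dropped: 2.65 / 20 = 13.3%
- 15 days dropped: 2.65 / 15 = 17.7%

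With equal arms of 254 / 2 = 127 (an assumption), 8.8% is about 11 patients and 17.7% about 22.

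**4. Smaller excesses (assumed, since the documents give none).**

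| Net excess | 30 days dropped | 15 days dropped |
|---|---|---|
| 2% | 0.6 days | 0.30 days |
| 5% | 1.5 days | 0.75 days |
| 10% | 3.0 days | 1.5 days |

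The net excess is the share on prescribed analgesics multiplied by the between-arm difference in the proportion of them switched. With 10% on prescribed analgesics and a 30-point difference, the shift is 0.10 × 0.30 × 30 = 0.9 days. It takes 30% and 30 points to reach 0.30 × 0.30 × 30 = 2.7 days. Both shares are assumptions.

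**The case against.** Five points on the other side have force.

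- **The label is loose only in places.** The hypotheses in both documents, the Protocol synopsis, SAP section 3 and shell Table S2 all speak simply of opioid use. This stands: the correction is confined to Protocol 9.2 and 9.4.2 and to any conclusion that borrows their wording.
- **Every participant has OUD.** Eligibility needs at least two DSM-5 symptoms or a recorded diagnosis, so some prescribed-opioid use may be part of the disorder. This weakens the mismatch against the SAP's construct of opioid use. It does not rescue the words illicit and illegal.
- **A reader might infer that the intervention is designed to move patients from analgesics to buprenorphine.** The documents do not support that. Protocol 6.1.1 describes starting MOUD for OUD; no section describes replacing or tapering a prescribed analgesic. Such a move is a possible consequence, of unknown frequency.
- **A reader might also infer a bias that always favours the intervention, or attach a false-positive rate to it.** Neither follows. Control providers may prescribe MOUD, referral may also lead to it, and the SAP's quoted item could push the other way. The SAP tests a baseline-adjusted contrast on the log-odds scale in a binomial mixed model, so day-scale arithmetic with assumed switch rates does not give that test's error rate.
- **The data for a sensitivity analysis may not exist.** The version 3 amendment entry says "we are now using chart review to identify prescriptions for opioids written in the primary care clinic", but the data sources listed in Protocol 8.1 and 10.1.8.1 do not mention chart review. The survey's Medication Use item is listed without its content. This stands, and makes that part of the remedy conditional.

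**Conclusion.** The concern holds as a mismatch between label and instrument, together with an unresolved difference between the two documents' versions of the item. As quoted in the Protocol, the item measures days of any opioid use other than MOUD taken as directed, and prescribed analgesics are included. It cannot alone support a statement about illicit use.

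A differential effect by arm is possible but not shown. Under the Protocol wording it would favour the intervention if moves from prescribed analgesics to MOUD were more frequent there. Under the SAP wording it could run against the intervention. The 8.8% and 17.7% figures only illustrate scale: they assume no difference in illicit use, the Protocol wording, a fall from 30 or 15 counted days to 0, and comparison on the mean-days scale. The share of participants on prescribed analgesics, the share who moved to MOUD, and the fielded instructions are all absent from the documents.

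**What to change.** 1. State which wording of item 7E was fielded, with any instruction given to respondents, and reconcile Protocol 9.4.2 with SAP section 3.
2. In Protocol 9.2 and 9.4.2, and in any conclusion, replace the illicit or illegal label with one that matches the fielded item. For the Protocol wording this could read: days of any opioid use other than MOUD taken as directed, including prescribed analgesics. Make no claim about illicit use from this item alone.
3. If baseline prescription data were collected, through chart review or the Medication Use items, report prescribed-analgesic status by arm in Table S1. Add to SAP 4.1 one sensitivity analysis of the opioid outcome that excludes patients with an opioid analgesic prescribed before consent. If outcome data have already been unmasked, label this analysis post hoc.

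Items 1 and 2 cost only wording. Item 3 costs one table row and one further model; that analysis has a smaller sample, so it should be read as supportive. If the prescription data do not exist, say so as a limitation.
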